#### **4.1 Inclusion Criteria**

Participants must meet all of the inclusion criteria to participate in this study.

- Children (males and females) between 11 and 16 years of age and their parent/primary caregiver will participate in the study.

##### Child Criteria

- Meets criteria for FAPD based on physician diagnosis of FAPD and ROME IV FAPD criteria (see *Description of Evaluations* section for additional details).
- Meets criteria for presence of clinically significant anxiety (based on the Screen for Child Anxiety Related Disorders [SCARED] total cut-off score  $\geq 25$ ; see *Description of Evaluations* section for additional details).

##### Child and Caregiver Criteria

- Youth and caregiver must have sufficient English language ability necessary to complete study measures and protocol.

#### **4.2 Exclusion Criteria**

All candidates meeting any of the exclusion criteria at screening will be excluded from study participation.

##### Child Criteria

- Children with a significant medical condition(s) with an identifiable organic cause including those that may include abdominal pain symptoms (e.g., Inflammatory Bowel Diseases).
- Children with a documented developmental delay(s), autism spectrum disorder, a previously diagnosed thought disorder (i.e., psychosis), or bipolar disorder.
- Significant visual, hearing, or speech impairment.
- Organic brain injury.
- Participants who are currently in psychological therapy for pain or anxiety.
- Participants with severe depressive symptoms (T score  $\geq 80$ ) or current active suicidal ideation reported on the CDI.
- Exclusionary criteria specific to the fMRI component of the study:
- Participants with an implant such as a cochlear implant device, a pacemaker or neurostimulator containing electrical circuitry or generating magnetic signals. Participants with any significant ferrous material in their body that could pose the potential for harm in the fMRI environment or cause signal suppression of key regions (i.e. orthodontia).
- Female participants who report current/suspected pregnancy.
- Participants with evidence of claustrophobia.

##### Child and Caregiver Criteria

- Inability or unwillingness of individual or legal guardian/representative to give written informed consent.

### 4.3 Study Enrollment Procedures

- **Method for identifying and recruiting candidates for the trial.** Eligible participants with FAPD will be identified for the study from new or existing patients seen at the outpatient pediatric GI clinics.
- **Procedures for documentation of reasons for ineligibility and for non-participation of eligible candidates.** A screening log will be maintained with eligible candidates contacted/approached for study recruitment. This log will detail reasons for ineligibility and/or reasons for disinterest in study participation if applicable. Once consented, participant names and ID numbers will be recorded in a secured enrollment log. A separate log will track participant progress throughout the study.
- **Consent procedures.** FAPD patients will be introduced to the study in person (or virtually if an in-person option is not available) by a medical staff member and/or study staff member who will explain the study to the patient and the primary caregiver in greater detail. Participants will be assured that their usual medical care will not be affected based upon whether or not they choose to participate. Written consent from the primary caregiver and written assent from the child will be obtained by study staff. All participants will be notified that screening is necessary and study entry is not guaranteed at this point. If the child is not eligible and the family is interested in the child receiving mental health services, contact information for the psychology service at HDVCH will be provided.
- **Randomization procedure for assigning a participant to an intervention group.** Following the baseline visit, patients will then be randomized to either the ADAPT group or a waitlist control group (each six weeks in duration) and will be informed of group assignment within a week of their baseline assessment, and will begin ADAPT/waitlist approximately one week after group assignment (with up to three weeks allowed to begin ADAPT). Gender and age will be used as blocking variables in randomization.

## 5. STUDY INTERVENTIONS

### 5.1 Interventions, Administration, and Duration

Participants will either begin ADAPT in the week following the treatment group assignment or after completing the post assessment (waitlist control). The duration of ADAPT is 6 weeks (although up to 8 weeks will be allowed for scheduling flexibility) and a total of 6 hours of intervention will be administered. Participants will be reminded via text message to complete their respective ADAPT web modules. Based on our prior research, the risk for potential for adverse events is low.

## **5.2 Handling of Study Interventions**

ADAPT will be primarily delivered by a trained interventionist ([name], licensed clinical psychologist). [name] is a trained provider with expertise in pediatric pain management and telehealth. In addition, a back-up provider will be available to deliver the intervention in the event of an absence of the primary provider.

## **5.3 Concomitant Interventions**

Any concomitant interventions (i.e., medical and psychological) experienced by the participants (either allowed or prohibited) will also be assessed for and recorded at baseline and post assessments. Participants will provide the reason and duration of concomitant interventions at the baseline and post assessment visits.

### **5.2.1 Allowed Interventions**

Participants are allowed to continue their medical care as usual (i.e., taking medication) throughout the duration of the study. Participants are also allowed to partake in psychological therapy as long as it is not directly addressing pain or anxiety.

### **5.2.2 Required Interventions**

There are no other required interventions.

### **5.2.3 Prohibited Interventions**

Youth who are currently in psychological therapy for pain or anxiety will be excluded from participation.

## **5.4 Adherence Assessment**

The projected sample size is not adequately powered to account for differences in adherence. However, data will be collected on the attendance of Zoom-based sessions, completion of web-based content, and completion of therapist videoconferencing/phone calls, in addition to completing study assessments. We anticipate good adherence (>80% completion of intervention materials) based on our prior research. If adherence becomes problematic during the course of the study, the interventionist ([name]) will communicate these concerns with the PI ([name]).

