## 3. STUDY DESIGN

- **Type/design of trial:** Masked clinical trial
- **Specific statement of the primary and secondary outcomes:** The primary outcome is that left AMY-PFC functional connectivity will be significantly reduced (i.e., decreased

hyperconnectivity) post ADAPT vs. waitlist. The secondary outcome is that brain activations associated with cognitive (PFC), affective (pgACC, AMY), and visceral afferent (INS, thalamus, aMCC, S1 & S2) pain will be significantly more diminished after ADAPT vs. waitlist. We will also explore whether changes in functional connectivity and brain activations following ADAPT correspond to reductions in pain (intensity and unpleasantness) and anxiety ratings.

- **Study population and groups/arms including sample size:** The target population is male and female youth between the ages of 11-16 with functional abdominal pain disorders (FAPD) and clinically significant anxiety. Youth will be recruited from pediatric gastroenterology clinics at Helen DeVos Children's Hospital. We aim to have between 17 – 25 participants in each arm for a total N of 34 - 50 participants in the study. Gender and age will be used as blocking variables in randomization.
- **Study location:** The study is located Helen DeVos Children's Hospital/Spectrum Health.
- **Approximate duration of enrollment period and follow-up:** Participants will be recruited from GI clinics and enrolled in the study during that visit (immediately). They will then come in for the baseline assessment, which will occur approximately one week after enrollment (though up to six weeks after enrollment will be allowed to account for MRI scanner availability). Following that visit, they will then be randomized to either the ADAPT group or a waitlist control group (each six weeks in duration) and will be informed of group assignment within a week of their baseline assessment, and will begin ADAPT/waitlist approximately one week after group assignment (with up to three weeks allowed to begin ADAPT). Up to eight weeks will be permitted for the six ADAPT sessions to account for potential scheduling conflicts and participant illness. Upon completion of ADAPT or waitlist control, participant outcomes will be reassessed at the post assessment visits (approximately six weeks after ADAPT/waitlist). After completing the post assessment visit, participants in the waitlist control group will be given the opportunity to complete ADAPT.

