#### **6.2.3 Blinding**

- **Procedure for retaining the blind.** Blinding of study personnel will be employed when possible (Table 1). Of note, our study statistician ([name]) will only have access to subject IDs and Treatment A and Treatment B. He will generate monitoring reports for closed sessions based only on Treatment A and Treatment B. If there is an issue of serious concern (e.g., safety issues in one arm, differential attrition etc.) that requires complete unblinding, [name] will identify another statistician to run the unblinded reports. [name] will also complete final analysis only by Treatment A versus B and the code will be revealed only after the data has been analyzed. Furthermore, the PI ([name]) will be blinded to group assignment. However, [name] will not be blinded to group assignment as study interventionist and to ensure the safety of participants and the integrity of the study. It is critical for [name] (a licensed clinical psychologist) to be aware of participants who are randomized to the ADAPT intervention to perform her role (and in the case of a back-up provider) to ensure patient safety (e.g., risk assessment for suicidal ideation, trauma/abuse, etc.) during the study. The PI ([name]) and study mentors ([name], [name]) will have no access to post-assessment data by group assignment until after the completion of the study.
- **Individual authorized to break the blind.** [name] will be authorized to break the blind. She will not be blinded to group assignment

and therefore can determine if the study team’s blind should be broken in cases where a patient’s safety is in question. [name] extensive experience as a pediatric psychologist make her appropriately equipped to manage this responsibility.

- **Circumstances for breaking the blind.** The blind will be broken at the clinical discretion of [name]. Circumstances for breaking the blind may include cases when a patient’s safety is at risk, differential attrition, or if a patient’s symptoms remarkably worsen throughout treatment.
- **Procedure for breaking the blind.** If the blind needed to be broken, [name] would communicate with our local IRB, any NCCIH members involved in the study, and involve our study team, included but not limited to the PI ([name]), co-mentors ([name], [name]), the biostatistician ([name]), and the outcome assessors (post-baccalaureate research coordinator).

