**Table 1. Blinding of Study Personnel.**

Stake holder	Intervention group assignment	Primary Mechanistic Outcome Measure	Clinical/ Functional Outcome Measure
Study subjects	Subjects will be aware if they are randomized to ADAPT versus waitlist.	The subjects will participate in the collection of this data but will not be involved in the interpretation of the data or the analysis of the results.	Subjects will provide such data. As such, they will be aware of their own responses on clinical/functional outcome measures.
Interventionists licensed clinical psychologist ([name]), backup interventionist	The interventionist will know if participants are randomized to the intervention group.	The interventionist will not be involved in analyses.	The interventionist will not be involved in analyses.
Outcome Assessors (post-baccalaureate research coordinator)	Outcome assessors will be blinded as to group assignment.	The outcome assessor will be involved in the collection of such data, but will not be involved in the interpretation and analysis of results.	The study coordinator will serve as an outcome assessor. However, data will be collected directly from participants using online forms. In addition, the study coordinator will only access/manage post-assessment data that has been de-identified (with group assignment removed).
Data Analysts/Statistician ([name])	The study statistician will be blinded to the group assignment.	The study statistician will be blinded until the completion of this study	The study statistician will generate reports and submit data as requested by NCCIH or the IMC

			for the duration of the study.
Principal Investigator ([name]) and Study Mentors ([name], [name])	The PI will be blinded to intervention group assignment.	The PI and her mentorship team will be blinded to post-assessment data results until after the completion of the analysis. She will participate in processing/management of fMRI data without knowledge of group assignment.	The PI and her mentorship team will be blinded to post-assessment results by group assignment until after completion of the analyses.

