## 7.3 Adverse Events and Serious Adverse Events

An **adverse event (AE)** is generally defined as any unfavorable and unintended diagnosis, symptom, sign (including an abnormal laboratory finding), syndrome or disease which either occurs during the study, having been absent at baseline, or if present at baseline, appears to worsen. Adverse events are to be recorded regardless of their relationship to the study intervention.

A **serious adverse event (SAE)** is generally defined as any untoward medical occurrence that results in death, is life threatening, requires inpatient hospitalization or prolongation of existing hospitalization, results in persistent or significant disability/incapacity, or is a congenital anomaly.

Adverse events and unanticipated problems will be carefully monitored and documented at each study visit. During all phases of the study (i.e., assessment and treatment), adverse events and unanticipated problems (whether or not they are thought to be study-related) will be monitored and documented in several ways.

1) During screening, assessments, and for those completing the ADAPT intervention, the interventionist ([name]) will maintain an individual log to record any increases in pain or mood-related problems during the study. [name] will review these logs each week.

2) In addition, the study team will have quarterly meetings to monitor the progress of the study, the integrity of the treatment, discuss the need for any protocol refinements, and conduct regular safety monitoring checks of adverse events and unanticipated problems. Severe depressive symptoms or active suicidal ideation will be recorded as an adverse event.

3) Any adverse events/unanticipated problems reported during the study including during the assessment (e.g., measures and fMRI/water loading) or during ADAPT sessions will be immediately brought to the attention of the study team. The IRB requires yearly renewal of study protocols, which provides additional monitoring of participant safety. The study team will review study data to ensure safety compliance and proper reporting to the IRB.

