## **7.4 Reporting Procedures**

Case report forms for AEs and SAEs have been developed. An AE documentation form will be completed by a clinician at the second ADAPT session and during the post assessment. For those randomized to waitlist control who are completing ADAPT after the post assessment, they will complete this information during session 2 and 6 of ADAPT in addition to the post-assessment query. The form documents whether or not an adverse event has occurred and throughout the trial if any AEs/SAEs are spontaneously reported by participants. AEs will be reported by body system and rated by level of severity (mild, moderate, severe, life-threatening). The primary study team will meet regularly to monitor the progress of the study and safety of participants in blinded fashion. Reportable events will also be recorded in a separate study database.

For any adverse event meeting the definition of “severe” or “life threatening,” the study interventionist ([name]) and research coordinator will communicate with one another to complete a “Serious Adverse Event” reporting form within one working day. Any severe or life threatening adverse event report will be sent to the IMC and the IRB will be notified.

To satisfy the requirement for prompt reporting, unanticipated problems will be reported using the following timeline:

- Unanticipated problems that are serious adverse events will be reported to the IRB, Independent Safety Monitor(s), and NCCIH within 7 days of the investigator becoming aware of the event.
- Any other unanticipated problem will be reported to the IRB, Independent Safety Monitor(s), and NCCIH within 14 days of the investigator becoming aware of the problem.

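### Three reporting rules, when triggered, can reveal a child's arm to the PI and the outcome assessor, both of whom the plan describes as blinded

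*Combined protocol and SAP*

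**What the plan says.** Section 3 labels the study a "Masked clinical trial". Table 1 in Section 6.2.3 sets out who is masked. Of the PI it says "The PI will be blinded to intervention group assignment" and, on the primary imaging outcome, "She will participate in processing/management of fMRI data without knowledge of group assignment". Of the assessors it says "Outcome assessors will be blinded as to group assignment". Sections 3 and 10.1 identify the assessor as the post-baccalaureate research coordinator. Participants and the interventionist know the assignment, and the plan says so openly.

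Three rules then move information from the treatment side to these people:

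- **Section 5.4.** If adherence becomes problematic, the interventionist "will communicate these concerns with the PI".
- **Section 7.4.** For a severe or life-threatening event, the interventionist and "research coordinator will communicate with one another to complete a" serious adverse event form within one working day.
- **Section 7.3.** Events reported at assessments or "during ADAPT sessions will be immediately brought to the attention of the study team".

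Section 6.2.3, repeated in Section 9.2, adds a procedure for breaking the blind. It involves the PI, the mentors, the statistician and the outcome assessors, and differential attrition is one of its triggers. The same section says that a different statistician would run unblinded reports if such an issue arose.

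**The concern.** ADAPT sessions, web modules and support calls take place before the post assessment in one arm only. A message that a particular child has missed sessions, or had an event in a session, therefore states that child's arm. The plan sends such messages to people whom its own table calls blinded. This is a conflict between rules, not just a missing detail.

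Families and the interventionist cannot be blinded in a waitlist comparison. Randomisation protects the allocation, but protection against bias in collecting and handling the outcome rests on the masking of staff. The primary outcome is a processed image, and the PI takes part in that processing. If the PI or the assessor learns some children's arms, the published description of the trial as masked would claim more than was delivered, and choices made while handling the scans would be open to challenge.

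**Working it through.** The plan states no figure on this point, so the check sets the rules beside the blinding statements.

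**1. Adherence concerns (Section 5.4).** Sender: the interventionist, unblinded under Section 6.2.3. Receiver: the PI, blinded under Table 1. The adherence data are session attendance, module completion and therapist calls, plus completion of study assessments. The first three exist before the post assessment only under ADAPT, so a child-level concern about them reveals the arm. An aggregate statement does not, nor does a concern about assessments, which both arms complete.

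**2. Serious adverse event forms (Section 7.4).** Sender: the interventionist. Receiver: the coordinator, who is the blinded assessor. Completing a form does not by itself show the arm, because Section 7 has the interventionist carry out risk assessments for any participant. A form or conversation that places the event in an ADAPT session does show it.

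**3. Session events (Section 7.3).** Receiver: the study team. The code-break procedure in Section 6.2.3 counts the PI and the assessors among that team. If the report names the setting and the child has not had the post assessment, the setting is the arm.

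**4. Masking steps.** None is written into these three rules. The safeguards stand elsewhere: safety meetings held blind (Section 7.4), data coded before analysis (Section 9.6), post-assessment data with group removed for the coordinator (Table 1), and a general qualifier that blinding applies where feasible (Section 6.2.3). Coding hides the label in a file. It does not undo what someone has been told about a child whose scan they can identify. Section 11.3 gives key study personnel the list linking names to IDs, without saying who they are.

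**5. Breaking the blind.** For differential attrition, one sentence of Section 6.2.3 hands the unblinded work to another statistician, while the code-break procedure brings in the PI, the statistician and the assessors. The two have not been reconciled.

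**6. How often (illustration only).** The documents give no rate. Let p be an assumed chance that an ADAPT child prompts at least one child-identified report to blinded staff, independent between children. Let n be the arm size: 17 to 25 in Section 3, and 20 as half of the total of 40 in Section 9.2. Then P(at least one report) = 1 − (1 − p)^n. For example, 1 − 0.95^20 = 1 − 0.358 = 0.642.

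| assumed p | n = 17 | n = 20 | n = 25 |
|---|---|---|---|
| 2% | 0.291 | 0.332 | 0.397 |
| 5% | 0.582 | 0.642 | 0.723 |
| 10% | 0.833 | 0.878 | 0.928 |
| 20% | 0.977 | 0.988 | 0.996 |

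At 5% or more, at least one such report is more likely than not. The expected number of children is smaller: 20 × 0.05 = 1.

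**The case against.** The strongest reply is that all three routes are conditional and may seldom be used. Section 5.4 can be read as concerning adherence across the trial, and it expects more than 80% completion. Section 7.4 applies only to severe or life-threatening events, and Section 7.1 expects no adverse events. The coordinator has little influence on the imaging result: questionnaires come directly from participants online, and Table 1 keeps the coordinator out of interpretation and analysis. The plan does not claim complete blinding. All of this stands, and it limits the point to what the rules can reveal when triggered. It does not remove the conflict, because nothing in the rules confines them to aggregate or arm-neutral content, and Table 1 does involve the coordinator in collecting the primary outcome data.

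A reader might go further in three ways that the documents do not support.

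- **The statistician is unblinded too.** Section 6.2.3 says "He will generate monitoring reports for closed sessions based only on Treatment A and Treatment B", and the session 2 adverse event query exists before the post assessment only under ADAPT. But no section says that these reports contain attendance or mark session 2 forms. The review of events by group in Section 9.4 may mean A versus B, and may go to the monitoring committee's statistician instead.
- **An unblinded statistician then picks covariates.** Section 9.6 leaves only exact age optional, and leaves that choice to unspecified personnel.
- **The bias can be sized from motion exclusions.** Section 4 expects about 10% of 45 children, or 4.5, to be lost to movement, and two shifted decisions would be 2/20 = 10% of an arm of 20. But no section says that the PI decides exclusions, and the two decisions are invented.

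**Conclusion.** The point holds in a limited form. The plan describes the PI and the research coordinator as blinded, yet three reporting rules can disclose a child's arm to them, and the safeguards found elsewhere are not built into those rules. The conclusion rests on three conditions: the report identifies the child, it carries session or module context, and it arrives before the post assessment. After that visit, waitlist children may also receive ADAPT, so session context no longer separates the arms by itself.

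Frequency is unknown, and the probabilities above follow entirely from the assumed p. No effect on the estimated treatment difference can be derived. This is a weakness in procedure that bears on the primary imaging outcome and is cheap to correct. It does not show that the blind will fail, and it does not invalidate the design.

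**What to change.** - **Section 5.4.** Give the PI aggregate adherence information only. Send child-level concerns to existing unblinded staff who neither assess outcomes nor process images. The Clinical Research Manager who holds the code (Section 9.2) is one candidate; because that role sits in a mentor's lab, bar onward disclosure to the mentors and the PI.
- **Sections 7.3 and 7.4.** Have unblinded staff complete the serious adverse event form. Send reports to the PI, the coordinator and the wider study team by subject ID, without arm-specific content. The monitoring committee, the IRB and any independent safety reviewer keep the full event context, and the existing reporting timelines stay as they are. Session 2 adverse event data should remain in the closed safety reports: removing them would weaken safety review in exchange for masking.
- **Sections 6.2.3 and 9.2.** Reconcile the team-wide code-break procedure with the provision for a separate statistician, in particular for differential attrition.
- **Table 1.** Keep the PI masked until image processing and exclusion decisions are finished. If the present routing is retained, state in the table the blinding actually achieved.

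The cost is revised wording in these sections and slightly more routing by existing staff, including for a form that is due within one working day. No new staff or data are needed.
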